## 2.2 Objectives

To evaluate safety and anti-tumoral effect of FLX475 combined with pembrolizumab in subjects with advanced or metastatic gastric cancer. The primary and secondary efficacies will be evaluated by RECIST 1.1 and iRECIST.

### 2.2.1 Primary objectives

To assess the anti-tumor efficacy of FLX475 in combination with pembrolizumab in subjects with advanced or metastatic gastric cancer by Objective Response Rate (ORR) by RECIST 1.1.

### 2.2.2 Secondary objectives

- To assess of the clinical efficacy including DCR (complete response + partial response + stable response), TTR, DoR, and PFS by RECIST 1.1
- To assess OS
- To assess of the clinical efficacy by iRECIST including iORR, iDCR, iTTR, iDoR, iPFS
- To assess the safety and tolerability of FLX475 combined with pembrolizumab based on Laboratory assessments and AE, SAE using NCI-CTCAE v 5.0

## 2.3 Endpoints

### 2.3.1 Primary endpoint

- Objective Response Rate (ORR, complete response + partial response) by RECIST 1.1

### 2.3.2 Secondary endpoints

- Efficacy in accordance with RECIST 1.1: DCR, TTR, DOR, PFS
- Efficacy in accordance with iRECIST: iORR, iDCR, iTTR, iDOR, iPFS
- Efficacy: OS

- Safety and tolerability: AEs, Laboratory assessments (including hematology, biochemistry, coagulation, urinalysis, vital signs, physical examination, ECG and ECOG)

[REDACTED]

[REDACTED]

[REDACTED]

## 2.4 Sample Size

[figure not shown]
There is little known about the objective response rate from the subjects who have progressed on at least 2 prior systemic treatments for advanced or metastatic gastric cancer excluding check point inhibitor (CPI). In addition, considering the study nature to explore the safety and efficacy by FLX475 and pembrolizumab, no formal statistical testing will be done. As stated in the study design part, each cohort will enroll target subjects separately and both cohorts will initiate 2-stage design. The initial number of target subjects for the 1st stage for both cohorts is determined as 10 based on feasibility. However, the target subject number for the 2nd stage would be determined based on the overall safety assessment and the posterior probability of at least 80% to achieve the ORR  $\geq 15\%$  and ORR  $\geq 30\%$  for cohort 1 and cohort 2, respectively.

The posterior probability for ORR  $\geq 15\%$  and ORR  $\geq 30\%$  for cohort 1 and 2, respectively, based on the responses in the first and second stage is described in the Table 11.1:1 and Table 11.1:2 below assuming uniform prior distribution for ORR. For example, if we observed 1 response out of the initial 10 subjects of cohort 1 at 1st stage followed by 6 responses out of additional 20 subjects at 2nd stage, we could assume that the probability of ORR  $\geq 15\%$  by FLX475 and pembrolizumab combination therapy would be 92% based on the observed data (Table 11.1:1). Also, if we observed 1 response out of the initial 10 subjects of cohort 2 at 1st stage followed by 7 responses out of additional 10 subjects at 2nd stage, we could assume that the probability of ORR  $\geq 30\%$  by FLX475 and pembrolizumab combination therapy would be 85% based on the observed data (Table 11.1:2).

[figure not shown]
Considering the minimum posterior probability of 80% to achieve ORR  $\geq 15\%$  for cohort 1 and  $\geq 30\%$  for cohort 2 as well as the overall safety data, the total number of subjects for each cohort will be adjusted after each stage.

- Prior distribution for ORR ( $P$ )  $\sim$  Unif (0,1)
- Observed data  $X \sim$  Binomial ( $N, P$ )
- Posterior distribution for ORR,  $(P| X) \sim$  Beta ( $1+X, 1+N-X$ ).
- **Table 11.1:1 Posterior probability of ORR  $\geq 15\%$  for Cohort 1 by number of subject and response**

[REDACTED]

- **Table 11.1:2 Posterior probability of ORR  $\geq 30\%$  for Cohort 2 by number of subject and response**

## 2.5 Randomization

Not applicable.

### 3. STATISTICAL CONSIDERATIONS

Data will be handled and processed per the sponsor's representative [REDACTED] Standard Operating Procedures (SOPs), which are written based on the principles of good clinical practice (GCP).

#### 3.1 General Considerations

All data collected on the electronic case report form (eCRF) will be presented in the data listings. In general, all data will be summarized with descriptive statistics for continuous endpoints (variables), and frequency and percentage for categorical endpoints (variables) unless other specified. As each cohort will enroll target subjects separately and so the analysis will be performed separately for each cohort as well. The data summaries will be presented by stage and overall across stages for each cohort.

Summary of treatment exposure, concomitant medication, pharmacokinetics, and all safety descriptive summaries will be presented by cohort.

Unless otherwise stated, the following methods will be applied:

- **Continuous variables**: Descriptive statistics will include the number of non-missing values (n), arithmetic mean, standard deviation (Sd), median, minimum and maximum values.

The minimum and maximum values will be displayed to the same decimal precision as the source data/eCRF data, the arithmetic mean and median values will be displayed to one more decimal than the source data for the specific variable. Sd will be displayed to two more decimal than the source data for the specific variable.

The appropriate precision for derived variables will be determined based on the precision of the data on which the derivations are based, and statistics will be presented in accordance with the above mentioned rules.

- **PK data**: For PK concentration data, the number of non-missing values, number of below limit of quantification (BLQ) values, arithmetic mean, standard deviation, median, minimum, maximum, coefficient of variation (CV%), geometric mean and geometric coefficient of variation (geo CV%) values will be presented. For the calculation of summary statistics, unrounded data will be used and reported to three significant figures with the exception of n, nBLQ, and CV% which will be presented to the nearest integer and one decimal place, respectively.

For PK parameter data, the number of non-missing values, arithmetic mean, standard deviation, median, minimum, maximum, CV%, geometric mean, and geo CV% values will be presented. Individual PK parameters will be presented to three significant figures with the exception of  $T_{max}$  which will be presented to two decimal places.

- **Categorical variables**: Descriptive statistics will include counts and percentages per category. The denominator in all percentage calculations will be the number of participants in the relevant analysis population with non-missing data, unless specifically stated otherwise. Percentages will be displayed to one decimal place. Proportions will be displayed to 3 decimal places.

95% Confidence Intervals (CIs) will be displayed to two decimal place for percentages. Proportions will be displayed to 3 decimal places. P-values will be displayed to 3 decimal places.

- **Time to Event Analysis**: Through the Kaplan-Meier (KM) method, nonparametric estimates of the survivor function will be represented by quartile estimates (Q1, Median and Q3) along with 95 CIs. Product limit estimates will be presented as part of appendices to the study outputs (SAS output).

KM plots of estimated survival/failure curves will be produced by cohort.

- **Repeat/unscheduled assessments**: Only values collected at scheduled study visits/time points will be presented in summary tables. If a repeat assessment was performed, the result from the original assessment will be presented as the result at the specific visit/time point. All collected data will be included in the data listings.

- Assessment windows: All assessments will be included in the data listings and no visit windows will be applied to exclude assessments that were performed outside of the protocol specified procedure windows.
- Result display convention: Results will be center aligned in all summary tables and listings. Subject identifiers visit and parameter labels may be left-aligned if required.
- Date and time display conventions: The following display conventions will be applied in all outputs where dates and/or times are displayed:

Date only: YYYY-MM-DD

Date and time: YYYY-MM-DD HH:MM

If only partial information is available, unknown components of the date or time will be presented as 'NK' (not known), i.e., '2016-NK-NK'. Times will be reported in military time.

### 3.2 Key Definitions

The following definitions will be used:

- Baseline: The baseline value is defined as the most recent non-missing measurements collected prior to the first study dose. Repeat and unscheduled assessments will be included in the derivation of the baseline values.
- Change from Baseline: The change from baseline value is defined as the difference between the result collected/derived at a post-baseline visit/time point and the baseline value.

The change from baseline value at each post-baseline visit/time point will be calculated for all continuous parameters using the following formula:

$$\text{Change from Baseline Value} = \text{Result at Visit/Time Point} - \text{Baseline Value}$$

The change from baseline value will only be calculated if the specific post-baseline visit/time point result and the baseline value for the parameter are both available and will be treated as missing otherwise.

- Study day: The study day of an event is defined as the relative day of the event starting with the date of the first study drug administration (reference date) as Day 1 (there will be no Day 0).

The study day of events occurring before the first study drug administration will be calculated as:

$$\text{Study Day} = (\text{Date of Event} - \text{Date of First Study Drug Administration})$$

For events occurring on or after Day 1, study day will be calculated as:

$$\text{Study Day} = (\text{Date of Event} - \text{Date of First Study Drug Administration}) + 1$$

Study days will only be calculated for events with complete dates and will be undefined for events that are 'Ongoing' at the end of the study.

Relative days compared to an alternative reference point will be calculated similarly, but the alternative starting reference start date will be used instead of the date of the first study drug dosing.

Study Day in months is calculated as Study Day in days divided by (365.25/12).

- End of study is defined as the date when the last subject, last visit occurs or the date at which all required follow-up data and documentation have been received by Sponsor, whichever occurs later.

### 3.3 Inferential Analyses

The time to event endpoints will be analyzed using the Kaplan-Meier survival analysis method. The survival functions of the time to event endpoints will be summarized for the 25th percentile, median, and 75th percentile and their 95% confidence intervals.

### 3.4 Multiple Comparisons and Multiplicity Adjustments.

Not applicable.

### 3.5 Handling of Missing Data

For the classification of Treatment emergent adverse event (TEAE) and Concomitant medication, the following will be applied in the following order:

- a. If all dates/times (start and stop) missing, the event/medication will automatically be classified as a TEAE/Concomitant medication.
- b. For AEs with a missing start date/time, if the event end date/time is prior to first study drug administration, the event will not be classified as a TEAE.
- c. If only the AE start year/ medication end year is present and is the same or is after the first study drug administration year unit, the event/medication will be classified as a TEAE/Concomitant medication.
- d. If the AE start month and year/medication end month and year are present and are the same or after the first study drug administration month and year units, the event/medication will be classified as a TEAE/Concomitant medication.

## Conversion of categorical values

In some instances, continuous variables are expressed as a range (i.e. < 10). In such cases, values may be converted to the range boundary (upper or lower limit as applicable). As an example, a value of <10 may be converted to 10. Such substitutions will be clearly documented in the footnotes of relevant outputs.

### 3.6 Coding of Events and Medications

Medical history and AE verbatim terms will be coded using the Medical Dictionary for Regulatory Activities (MedDRA) using the latest version available at the time of study commencement, graded using NCI-CTCAE version 5.0. Terms will be coded to the full MedDRA hierarchy, but the system organ class (SOC) and preferred terms (PT) will be of primary interest for the analysis.

Prior and concomitant medications will be coded using the World Health Organization Drug Dictionary (WHO-DD) using the latest version available at the time of study commencement. Medications will be mapped to the full WHO-DD Anatomical Therapeutic Chemical (ATC) class hierarchy, but Anatomical

Therapeutic Chemical (ATC) class Level 3 and preferred name (PN) will be of primary interest in this analysis.

### 3.7 Cohorts/Stages

- Cohort 1: Checkpoint inhibitor naïve Epstein-Barr Virus (EBV) negative gastric cancer subjects who have progressed on at least 2 prior systemic treatments for advanced or metastatic gastric cancer
  - Stage 1 (at least 10 subjects)
  - Stage 2 (20 subjects + up to additional 30 subjects)  
→ Maximum No. of subjects: 60 subjects
- Cohort 2: Checkpoint inhibitor naïve EBV positive gastric cancer subjects who had at least 1 prior systemic treatment for advanced or metastatic gastric cancer
  - Stage 1 (10 subjects)
  - Stage 2 (10 subjects + up to additional 10 subjects)  
→ Maximum No. of subject: 30 subjects

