5. STUDY DESIGN

5.1. Overall Design and Plan

This clinical study is a Phase 2, open-label study to assess the efficacy, safety profile of FLX475 combined with pembrolizumab in patients with advanced or metastatic gastric cancer. Approximately 90 subjects may be enrolled across two cohorts to examine the safety and efficacy. This study is designed to assess the potential anti-tumor activity when administered at the 100mg QD of FLX475 with pembrolizumab and will be conducted (2) cohorts as detailed below.

Cohort 1: Checkpoint inhibitor naïve Epstein-Barr Virus (EBV) negative gastric cancer subjects who have progressed on at least 2 prior systemic treatments for advanced or metastatic gastric cancer

Cohort 2: Checkpoint inhibitor naïve Epstein-Barr Virus (EBV) positive gastric cancer subjects who had at least 1 prior systemic treatment for advanced or metastatic gastric cancer

Cohort 1 will be enrolled in two stages, starting with at least 10 subjects in the first stage. Expansion to the stage 2 of cohort 1 will be based on the overall safety and efficacy data as well as any available PK and PD data when the 10th subject completes 4 cycles (or 12 weeks; after 2nd response assessment) or withdrawn from the study, whichever occurs first. During this data review, Sponsor can determine study discontinuation if there is no responder from 10 subjects in the first stage. Once expanded, 20 additional subjects will be accrued in stage 2 and further assessment for the safety and efficacy based on the accumulated data up to 30 subjects (10 from stage 1 and 20 stage 2) will be performed. Referring to the published data[11], 15% of ORR is the minimum criteria to proceed for the next stage in the study. If the posterior probability for the ORR $\geq 15\%$ is less than 80%, the enrollment to the cohort will be paused and assessed overall safety along with PK and PD data available. In consideration of the cumulative overall safety and efficacy up to the 30 subjects along with the other competitive landscape, the cohort 1 could be expanded further up to 60 subjects at maximum including the previous subjects enrolled or could be stopped for further enrollment. Also, if required, there could be another stage to investigate further after 2nd stage as well.

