### 12.1 Tumor Assessment

Best overall response is the best response recorded from the treatment start date until the earliest of disease progression or last evaluable tumor assessment before events such as start of new anticancer therapy, death, lost to follow-up, etc. Objective response rate (ORR) is defined as the proportion of subjects whose confirmed best overall response is either Complete Response (CR) or Partial Response (PR) according to RECIST version 1.1. Disease control rate (DCR) is defined as the proportion of subjects with confirmed best overall response of CR, PR or SD according to RECIST version 1.1.

The hierarchy used to determine best overall response is CR>PR>SD>PD. [REDACTED]

The progression date is the earliest date among all images of PD lesion. If a subject does not experience PD in one disease assessment, his/her non-PD date will be the latest date among all images of the disease assessment.

Overall best response categories (including: CR, PR, PD, SD), ORR and DCR will be summarized (categorical descriptive analysis), together with the two-sided exact (Clopper-Pearson) 95% confidence intervals.

Based on the cumulative data about ORR along with prior assumption at each stage, posterior probability of ORR  $\geq 15\%$  for cohort 1 and ORR  $\geq 30\%$  for cohort 2 would be computed to determine go/no-go decision of the next stage. This cumulative data analysis will be implemented only if at least one response is observed from stage 1 of each cohort.

According to iRECIST, Best Overall Response (iBOR) of complete response (CR/iCR), partial response (PR/iPR), stable disease (SD/iSD), Progressive disease (iPD) or unevaluable (iUE) will be derived. iORR, iDCR, iTTR, iDoR and iPFS will be analyzed in the same manner as used analyses in accordance with RECIST 1.1. iPD is defined as the time point of first iUPD without subsequent iSD, iPR or iCR before study treatment discontinuation.

For the sum of diameter in target lesion, percent change from baseline at each scheduled tumor assessment time-point and maximal tumor shrinkage from baseline during the study will be summarized.

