## **16. INTERIM AND FINAL ANALYSIS**

### **16.1 Interim Analyses**

The study is planned initially for 2-stage design for both cohorts but there might be more than 2 stages depending on the results for each cohort. Based on the initial plan with 2-stage design, the interim analysis for each cohort will be performed when the initial 10 subjects of each cohort completes 4 cycles (or 12 weeks; after 2nd response assessment) or withdrawn from the study, whichever occurs first. At this time both efficacy and safety results as well as any available PK and PD data will be reviewed by the IDMC. The number of subjects for the next stage will be determined based on the interim data analysis as well. Study discontinuation due to futility may be recommended by the IDMC to the Sponsor. More details about the decision making based on the interim analysis will be described in charter.

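### SAP 3.7 gives one 'Stage 2' label to subjects enrolled before and after the 30-/20-subject go/no-go review, so the by-stage ORR mixes the two

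*SAP*

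**What the plan says.** In Protocol 5.1 the second stage of Cohort 1 is a fixed block: "Once expanded, 20 additional subjects will be accrued in stage 2". A review follows, in which an assessment on "accumulated data up to 30 subjects (10 from stage 1 and 20 stage 2) will be performed". If the posterior probability that ORR is at least 15% is below 80%, enrolment is paused. After that review, "the cohort 1 could be expanded further up to 60 subjects at maximum including the previous subjects enrolled". Cohort 2 has the same structure with 10 more subjects, a review at 20, a 30% bar and a ceiling of 30. SAP 2.1 repeats both descriptions. Both documents add, in a separate sentence, that a further stage after the second is possible.

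SAP 3.7 sets the labels used for analysis. Cohort 1 has "Stage 2 (20 subjects + up to additional 30 subjects" and Cohort 2 has "Stage 2 (10 subjects + up to additional 10 subjects".

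The labels govern reporting. SAP 3.1 states: "The data summaries will be presented by stage and overall across stages for each cohort". The statistical methods in the protocol synopsis say that ORR and DCR are summarised by stage with Clopper-Pearson intervals. SAP 12.1 says that the posterior "would be computed to determine go/no-go decision of the next stage". SAP 16.1 describes one interim in detail: "the interim analysis for each cohort will be performed when the initial 10 subjects of each cohort completes 4 cycles", or 12 weeks, or withdrawal.

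**The concern.** In SAP 3.7 the go/no-go review falls inside a stage instead of between stages. At full size, 20 of the 50 'Stage 2' subjects in Cohort 1 (40%) and 10 of the 20 in Cohort 2 (50%) belong to the data that decided whether the cohort would grow. Given that it did grow, their response rate is expected to lie above the true rate. Subjects enrolled after the decision are not affected by the rule, but in a pooled 'Stage 2' row they cannot be seen on their own.

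This is a single-arm trial with no formal test, and its main product is a descriptive ORR. A reader who takes 'Stage 2' as fresh data that confirm Stage 1 would be misled.

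A related gap is that the visible text sets no follow-up condition for the 30-/20-subject look like the one set for the first look. The denominator at that look is therefore open.

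**Working it through.** **Inputs.** From Protocol 11.1 and SAP 2.4: uniform prior, posterior Beta(1+X, 1+N−X), 80% criterion, thresholds of 15% and 30%. From Protocol 5.1 and SAP 3.7: blocks of 10, 20 and up to 30 (Cohort 1), and 10, 10 and up to 10 (Cohort 2). Assumptions: the true ORR (shown as a range), at least one response in Stage 1 needed to continue, the 80% rule binding, and expansion to the maximum.

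**Step 1. Reproduce the plan's figures.** P(ORR ≥ t | X, N) = 1 − F(t; 1+X, 1+N−X), with F the Beta distribution function.
- Cohort 1, 7/30, t = 0.15, Beta(8, 24): 0.918 (plan: 92%).
- Cohort 2, 8/20, t = 0.30, Beta(9, 13): 0.852 (plan: 85%).

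**Step 2. Smallest count that meets 80%.**
- Cohort 1: 5/30 gives 0.683 and 6/30 gives 0.827, so the boundary is 6/30.
- Cohort 2: 7/20 gives 0.723 and 8/20 gives 0.852, so the boundary is 8/20.

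**Step 3. Expected ORR given expansion.** Let A ~ Bin(n1, p) be Stage 1 responses and B ~ Bin(n2, p) be responses in the pre-decision part of Stage 2. Enumerate all (A, B) with A ≥ 1 and A + B at or above the boundary. This gives E1 = E(A)/n1 and E2 = E(B)/n2 on that set. The post-decision block of n3 subjects has expectation p. Then:
- SAP 'Stage 2' = (n2·E2 + n3·p)/(n2 + n3)
- Overall = (n1·E1 + n2·E2 + n3·p)/(n1 + n2 + n3)

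Cohort 1 at p = 0.15 (probability of expansion 0.276): E1 = 0.2414, E2 = 0.2260.
- 'Stage 2' = (4.520 + 4.500)/50 = 18.0%
- Overall = (2.414 + 4.520 + 4.500)/60 = 19.1%

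Cohort 2 at p = 0.30 (probability of expansion 0.228): E1 = 0.4407, E2 = 0.4406.
- 'Stage 2' = (4.406 + 3.000)/20 = 37.0%
- Overall = (4.407 + 4.406 + 3.000)/30 = 39.4%

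| Cohort | True ORR (= post-decision block) | Pre-decision part of Stage 2 | SAP 'Stage 2' | Overall |
|---|---|---|---|---|
| 1 | 10% | 21.1% | 14.4% | 15.8% |
| 1 | 15% | 22.6% | 18.0% | 19.1% |
| 1 | 20% | 24.7% | 21.9% | 22.6% |
| 1 | 25% | 27.5% | 26.0% | 26.4% |
| 1 | 30% | 31.2% | 30.5% | 30.7% |
| 2 | 20% | 42.1% | 31.0% | 34.7% |
| 2 | 30% | 44.1% | 37.0% | 39.4% |
| 2 | 40% | 47.4% | 43.7% | 44.9% |
| 2 | 50% | 52.8% | 51.4% | 51.8% |

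Dropping the Stage 1 condition changes little: 'Stage 2' is 18.2% at true 15% in Cohort 1 and still 37.0% at true 30% in Cohort 2.

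**Step 4. What pooling can hide.** Take the protocol's own example, 6/20 in Stage 2, and assume 3/30 after the decision. The two blocks are 30% (95% CI 11.9 to 54.3) and 10% (2.1 to 26.5). Under SAP 3.7 they appear only as 9/50, 18% (8.6 to 31.4).

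**Step 5. Follow-up at the second look.** Suppose 5 responses have been seen when only 25 of the 30 Cohort 1 subjects have been scanned (an assumed count). Then 5/25 gives 0.815, which meets the criterion, and 5/30 gives 0.683, which does not. The choice of denominator decides the outcome.

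**The case against.** **SAP 3.7 does not clearly contradict the protocol.** The protocol mentions the expansion first and then, as an addition, the possibility of another stage. Treating the expansion as a continuation of Stage 2 is a permissible reading. This stands: the SAP resolves an ambiguity, and does so in the less informative way. It is also a reason not to call the expansion Stage 3, a name that the separately reserved later stage may need.

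**A reader might infer that the post-decision subjects are never shown separately.** That cannot be verified. The table and figure lists are redacted, there is a redaction in SAP 12.1, and SAP 12.3 has no visible content. The supportable statement is that no visible text specifies the split.

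**A reader might infer that the second look has no trigger.** It has one: Protocol 5.1 and SAP 2.1 place it at 30 and 20 cumulative subjects with the 80% rule, and further decision detail is left to a charter. Only a follow-up condition is missing from the visible text.

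**The effect is conditional.** Enrolment is paused rather than stopped, and safety, PK/PD and the competitive landscape also count. The upward shift exists only given expansion. Averaged over all paths of the same enumeration, the overall ORR is expected below the true rate: 11.9% against 15%, and 28.5% against 30%. This stands, but a 'Stage 2' row of 50 or 20 subjects exists only after expansion, so the conditional figure is the one that bears on it.

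**The practical gain is limited.** Stage 1 stays separate, an overall summary is planned, listings would allow a later split, and the Cohort 2 post-decision block has at most 10 subjects (3/10 has a 95% CI of 6.7 to 65.2%). All true, but a split specified before database lock carries more weight than one made after the data are seen.

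**Conclusion.** The point holds as a matter of estimation and reporting. If a cohort is expanded, the SAP 'Stage 2' ORR combines decision-triggering and post-decision subjects. Its expected excess over the true rate is 3.0 percentage points at true 15% and 1.0 at true 25% in Cohort 1, and 7.0 points at true 30% and 1.4 at true 50% in Cohort 2. These figures assume a binding 80% rule, at least one Stage 1 response and full expansion. Without expansion beyond 30 or 20 subjects the issue does not arise.

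Two stronger conclusions are tempting and are not supported. First, this is not a type I error problem, because SAP 2.4 rules out formal testing. Relabelling also does not correct the overall ORR, which carries the same selection. Second, the lack of a stated posterior at the final 60 or 30 subjects is not a defect. SAP 12.1 uses the posterior for go/no-go decisions on the next stage, and applying it to the final data would add a success criterion that the trial never set.

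**What to change.** - **SAP 3.7:** split Stage 2 into a pre-decision block (20 in Cohort 1, 10 in Cohort 2) and a post-decision expansion (up to 30, up to 10), for example 2a and 2b.
- **SAP 12.1:** report ORR with a Clopper-Pearson 95% CI for the post-decision block beside the overall ORR. Note that the overall figure includes the subjects on whom the decision was based.
- **SAP 16.1:** list the 30-/20-subject look as an analysis. Apply the first look's follow-up condition (4 cycles or 12 weeks, or withdrawal) to every subject counted.
- Do not add a posterior success criterion at the final sample size.

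The cost is SAP wording and one extra table column. The post-decision estimate will be imprecise, especially in Cohort 2, and may look less favourable than the pooled figure. Enrolment numbers and eligibility do not change. The second look may come somewhat later, because every subject counted must first meet the follow-up condition.
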